7.1.6.2. Oral Corticosteroid Taper

Starting on Day 15, patients will begin a taper (reduction) in OCS (per the ATYR1923-C-002 Oral Corticosteroid Taper Guidelines) from their starting dose of 10-25 mg/day of prednisone (or equivalent) to a target dose of 5 mg/day, to be completed on or before Day 50. The OCS dose will be tapered by 5.0 mg/day every 1 to 2 weeks, depending on the starting dose. Smaller incremental titrations to the target dose of 5 mg/day by Day 50 may be implemented per Investigator judgement. Patients will be maintained at the target dose of 5.0 mg/day (or equivalent) through Week 24/EOS. Optionally, further titrations in the OCS dose to below 5 mg/day may be attempted after the Week 16 visit, if determined by the Investigator to be feasible.

Patient will document OCS doses in a diary, which will be reviewed at relevant scheduled telephone contacts and study visits.

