3.3. Summary of Statistical Analysis Changes to the Protocol

The PK Concentration Parameter Analysis Set included in the protocol, Section 10.1.1.4, is not included in this SAP. Instead, an Efficacy Evaluable Set has been added. The Intent to Treat (ITT) Analysis Set is included in the Protocol, Section 10.1.1.1. However, due to the possibility of subjects who have been randomized but not dosed, a modified Intent-to-Treat (mITT) population is used in the SAP.

aTyr Pharma, Inc.
Study ATYR1923-C-002 Statistical Analysis Plan
IND#: 133692

FINAL Version 1.0
2021-08-02

The first secondary endpoint specified in the protocol specifies the following.

- Total cumulative steroid dose administered over the primary study period (Day 1 through Week 24) by treatment cohort

During planning of this analysis, it was brought to attention that subjects may be dosed for different periods of time, and visits may occur at different study days for different subjects due to scheduling conflicts. Therefore, a time adjusted AUC will be used to examine OCS use.

In the protocol secondary endpoints below are specified for Week 24 visit.

- Total cumulative steroid dose administered over the primary study period (Day 1 through Week 24) by treatment cohort
- Number of patients who achieve the targeted tapered dose of prednisone 5 mg/day (or equivalent) and maintain it through Week 24 by treatment cohort

In light of the half-life of the investigational product, it was decided that the endpoints will be examined for the end of dosing period instead. The end of dosing period is defined as 30 days after the last dose.

In addition, due to protocol prescribed taper prior to Day 51, an additional period, Day 51 through end of dosing interval, will also be examined, together with Day 1 through end of dosing interval.

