10.1.1. OCS Data Sources

The sources of OCS use are summarized in the table below.

Time of Use	Data Source	CRF Name	Comments
Historical and current use at Screening	OCS LOG	OCS Log - Prior and Current Use table	Historical use will be added here. An additional row for every change in steroid or dose
Steroid use beginning on Day 1	eDiary	Patient Diary	Patients will be entering a form every day and from that data we can pull out any dosing changes or changes in use
	OCS LOG (for subjects who do not have eDiary)	OCS Log - Prior and Current Use table	Study Coordinators will be responsible for recording any dosing changes or changes in steroid use in this table based on the paper diaries completed by the subject

aTyr Pharma, Inc.
 Study ATYR1923-C-002 Statistical Analysis Plan
 IND#: 133692

FINAL Version 1.0
 2021-08-02

Changes in Dose	eDiary and OCS LOG for subjects without eDiary	Patient Diary and OCS Log - Prior and Current Use table	
-----------------	--	---	--

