10.1.4. Study Drug Adjusted OCS Burden

Since a missed dose in study treatment is likely to affect OCS dose, in order to isolate the effect of treatment, the above mentioned OCS dose, change from baseline and percent change from baseline analyses will be repeated, but excluding a window around a missed dose of study treatment, where a window is defined as 30 days after the previous dose and restart on the day of the next administered dose. Active treatment and placebo will be compared in the same way as in time adjusted OCS burden in the previous section.

10.1.5. Achievement of Target Taper Dose of Prednisone 5 mg/day (or Equivalent) and Maintained Through Week 24

The number and percentage of patients who have achieved the following will be summarized.

1. **Ability to Taper:** Taper OCS dose level down to 5mg/day or less at any time and remained for at least 5 consecutive days.
2. **Maintain Taper:**
 - a. Taper OCS dose level down to 5mg/day or less at any time and remained for at least 30 consecutive days.
 - b. Taper OCS dose level down to 5mg/day or less at any time and remained for at least 60 consecutive days.
 - c. Taper OCS dose level down to 5mg/day or less at any time and remained for at least 90 consecutive days.
 - d. Taper OCS dose level down to 5mg/day or less at any time and remained for at least 115 consecutive days

- e. Time to first relapse of taper for sarcoidosis. Defined as the duration from the first day of hitting 5mg (plus 5 consecutive days) to when >5mg is needed. If the reason for increase in OCS is unrelated to sarcoidosis (as identified from the eCRF) then that episode will not count as a relapse and counting of the duration will recommence on the next day on which 5mg is achieved. For patients who maintain 5mg after successful taper will be censored at 30 days after last dose or EOS (if earlier). Patients who never reach 5 mg will be assigned a duration of 1 day and be classified as a censored data point.
- f. Proportion of days at 5mg or less ignoring diary days when OCS dose was increased >5mg for non-sarcoidosis events (i.e. same exclusion as the Time to First Relapse endpoint)
- g. Proportion of days at 5mg or less including all diary days (i.e. even those when OCS dose was increased >5mg for non-sarcoidosis events)

In each of the above endpoints, when study drug dosing is missed, OCS diary data >30 days after previous study drug infusion will be ignored until dosing restarted as described in Section 10.1.4.

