For each of the first 4 taper maintenance endpoints above, 2-sided Fisher's exact test will be performed between each individual active treatment arm and combined placebo, using the pseudo code below.

```
proc freq data = taper (where=(treatment in ("Treatment A", "Placebo")));
  table taper_var*treatment / fisher;
run;
```

For the 5th of the "Maintain taper" endpoints (i.e. Time to first relapse of taper), Kaplan-Meier methods will be used to derive estimates of median (& 95% CI) of the time to first taper relapse. A log-rank test will be performed between each individual/combined active treatment arm and placebo to obtain p-values versus placebo. Kaplan-Meier curve will be presented as well. The following pseudo SAS code is used.

```
proc lifetest;
  time duration*status(0);
  strata treatment / test=logrank;
run;
```

where 0 indicates no relapse.

For 6th and 7th of the "Maintain taper" endpoints (i.e. Proportion of days at 5mg or less) descriptive statistics (Mean, SD etc) will be used to informally compare groups. A Wilcoxon rank sum test will be performed between each individual/combined active treatment arm and placebo to obtain p-values versus placebo. The following pseudo SAS code will be used.

aTyr Pharma, Inc.
Study ATYR1923-C-002 Statistical Analysis Plan
IND#: 133692

FINAL Version 1.0
2021-08-02

```
proc nparlway wilcoxon correct=no;  
  class treatment;  
  var days_at_5mg;  
  exact wilcoxon;  
run;
```

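### SAP 10.1.5 items 2f and 2g (proportion of days at 5 mg or less) have no stated start day and no adjustment for starting dose, so equally successful tapers can score anywhere from about 71% to 92%

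*SAP*

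**What the plan says.** Protocol 7.1.6.2 keeps patients on their entry dose of 10-25 mg/day for two weeks: "Starting on Day 15, patients will begin a taper (reduction) in OCS". The target of 5 mg/day is due by Day 50, and the pace varies: "The OCS dose will be tapered by 5.0 mg/day every 1 to 2 weeks, depending on the starting dose". Smaller steps are allowed at the investigator's judgement.

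SAP 3.3 recognises what this does to a steroid measure: "due to protocol prescribed taper prior to Day 51, an additional period, Day 51 through end of dosing interval, will also be examined". SAP 4.2.2 and 10.1.3 then apply the Day 51 window to the time-adjusted AUC and to no other endpoint. The AUC model in 10.1.3 also carries baseline OCS as a covariate.

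SAP 10.1.5 lists two day-count measures among its taper-maintenance endpoints. Item 2f is the "Proportion of days at 5mg or less ignoring diary days when OCS dose was increased >5mg for non-sarcoidosis events". Item 2g is the "Proportion of days at 5mg or less including all diary days". Neither has a start day or a defined denominator. The only other exclusion is of diary data more than 30 days after an infusion when a study dose is missed. SAP 10.1.1 gives the diary (or the OCS log, for patients without an eDiary) as the source for "Steroid use beginning on Day 1". The planned comparison is: "A Wilcoxon rank sum test will be performed between each individual/combined active treatment arm and placebo to obtain p-values versus placebo". Its code has treatment as the only factor and names the variable `days_at_5mg`.

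Randomisation is 2:1 within each cohort of 12. Neither document mentions stratification by starting dose.

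**The concern.** A maintenance endpoint should give the same score to two patients who taper as scheduled and stay at 5 mg. If the count starts on Day 1, these endpoints do not. No patient can be at 5 mg before Day 15 while following the schedule, and after that the date depends largely on starting dose and step interval. Variation unrelated to study drug enters the score, and the test does nothing to remove it. The SAP corrected the AUC for the same problem and left these companion endpoints as they were.

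Steroid-sparing is a secondary objective. The comparisons are of 8 patients per dose, or 24 combined, against 12 pooled placebo patients. At those sizes, the added spread can hide a difference, and a chance imbalance in starting dose can produce one.

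**Working it through.** The documents give no power calculation or expected value for these endpoints, so there is no planned figure to reproduce. The check applies the SAP's definitions to a patient who follows the taper and never relapses.

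**Inputs.** Starting dose 10, 15, 20 or 25 mg/day, first reduction on Day 15, 5 mg steps every 1 or 2 weeks, 5 mg due by Day 50 (Protocol 7.1.6.2). End-of-study visit on Day 169 (Protocol Table 1). End of dosing period = last dose + 30 days (SAP 3.3), which is 141 + 30 = Day 171 after six doses.

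**Proportion of days at 5 mg or less.** If 5 mg is first reached on day r and the window ends on day N, the Day 1 score is (N - r + 1)/N. With N = 169:

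| Start and pace | r | From Day 1 | From Day 51 |
|---|---|---|---|
| 10 mg, one step on Day 15 | 15 | 155/169 = 91.7% | 119/119 = 100% |
| 15 mg, weekly | 22 | 148/169 = 87.6% | 100% |
| 20 mg, weekly | 29 | 141/169 = 83.4% | 100% |
| 25 mg, weekly | 36 | 134/169 = 79.3% | 100% |
| 20 mg, 2-weekly | 43 | 127/169 = 75.1% | 100% |
| Any start, 5 mg first reached on the last permitted day | 50 | 120/169 = 71.0% | 100% |

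With N = 171 the range is 157/171 = 91.8% to 122/171 = 71.3%. A 10 mg starter could therefore spend 155 - 134 = 21 days back above 5 mg and tie with a 25 mg weekly starter who never relapsed. Against a patient first reaching 5 mg on Day 50, the figure is 155 - 120 = 35 days.

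**Effect on the test (illustrative; inputs assumed).** 24 active against 12 placebo, two-sided 0.05, asymptotic Wilcoxon test, 4,000 runs. Weekly tapers; starting doses spread evenly over 10/15/20/25 mg except in the last row. Every relapse falls after Day 50 and lasts to Day 171, an assumption that favours the Day 51 window.

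| Scenario | Rejection, Days 1-171 | Rejection, Days 51-171 |
|---|---|---|
| Relapse 20% active, 60% placebo | about 44% | about 65% |
| Relapse 20% active, 70% placebo | about 64% | about 82% |
| Relapse 40% in both, same dose mix | about 4.5% | about 4.8% |
| Relapse 40% in both, dose mix 40/30/20/10% active, 10/20/30/40% placebo | about 18.5% | about 4.8% |

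**Day 1 time-adjusted AUC.** 20 mg start, weekly steps, trapezoidal formula of SAP 10.1.3. The area from Day 1 to Day 29 is 13×20 + 17.5 + 6×15 + 12.5 + 6×10 + 7.5 = 447.5, and each later day adds 5.

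- To Day 169: (447.5 + 140×5)/168 = 6.83 mg/day.
- Four doses, last on Day 85, window to Day 115: (447.5 + 86×5)/114 = 7.70 mg/day.
- One dose, window to Day 31: (447.5 + 2×5)/30 = 15.25 mg/day.

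One such patient among 8 moves the arm mean by (7.70 - 6.83)/8 = 0.11 mg/day in the four-dose case and (15.25 - 6.83)/8 = 1.05 mg/day in the one-dose case. The Day 51 AUC is 5.00 mg/day for every perfect taper.

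**The case against.** **The Day 1 start is inferred.** The reference to all diary days in 2g mainly contrasts it with 2f; it does not set a window. SAP 3.3 lists the achieve-and-maintain endpoint beside the cumulative dose before adding the Day 51 period, so the sponsor may have meant it for both. This stands as a limit on the claim: the exact defect is an undefined window. It does not remove the defect, because 4.2.2 and 10.1.3 give Day 51 to the AUC only, and a programmer following 10.1.5 would count from the first diary day.

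**Days 15-50 are informative.** Smaller steps are permitted (Protocol 7.1.6.2) and rescue is available (7.1.6.3), so a slow or interrupted taper says something about the patient. This stands. Only Days 1-14 are fixed for everyone, and it is a reason to keep an all-days version.

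**It is noise, not bias.** With the same dose mix and no effect, the rejection rate stays near 5%. The 18.5% figure needs a strong assumed imbalance. This also stands, as does the exploratory status: SAP 7.4.1 rules out formal hypothesis testing, and time to first relapse (2e) already starts once 5 mg is reached.

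**The AUC.** A reader might infer that the Day 1 AUC is equally at fault, particularly as SAP 3.3 adopts time adjustment because "subjects may be dosed for different periods of time". The documents do not support that. The SAP names the taper problem, adds the Day 51 AUC, puts baseline OCS in the model, and repeats the OCS analyses in the EE Set, which requires at least four doses. The 15.3 mg/day case can arise only in the mITT Day 1 analysis. Dropping the Day 1 comparison or replacing its model would be a trade-off, since Day 1 through Week 24 is the protocol's own period for cumulative steroid dose.

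**Conclusion.** The point holds for items 2f and 2g. As written, their window is undefined. On the natural reading it includes the days before and during the scheduled taper, and the test ignores the starting dose that the AUC model adjusts for. Equally successful patients then differ by about 20 percentage points (71.0% to 91.7% over Days 1-169), and the difference vanishes from Day 51.

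Those figures rest on a perfect taper with no relapse and full follow-up. The consequence is lost precision when starting doses are balanced, and a possible distortion when they are not. The documents do not show that an imbalance occurred, so a conclusion that the planned comparison is biased would go too far.

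For the AUC, one caution remains: in the mITT Set the Day 1 value rises as the window shortens (6.8, 7.7 and 15.3 mg/day in the examples), so it should be read beside the Day 51 and EE results.

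**What to change.** 1. In SAP 10.1.5, define the tested version of 2f and 2g over Day 51 to the end of the dosing interval, matching SAP 3.3 and 10.1.3.
2. Define the variable as a proportion, with numerator and denominator stated. The code name `days_at_5mg` could be taken as a raw count, which would depend even more on length of follow-up.
3. Keep the all-days version as supportive, adjusted for baseline OCS: for example, rank ANCOVA on baseline dose, or a van Elteren test by baseline OCS. The 10 against >10 mg/day split in SAP 10.1.7 could supply the strata, but it pools 15, 20 and 25 mg starters, whose perfect-taper scores still differ (87.6% to 79.3% with weekly steps).
4. Report by arm the number of patients with no days from Day 51 onward.
5. Beside the mITT Day 1 AUC, add a note that it depends on window length. No change of model is needed.

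The cost is SAP wording and minor programming, with no new data. The downside is that patients whose window ends before Day 51 drop out of the tested version. With dosing on schedule these are patients who had one infusion only: a window from a last dose on Day 29 runs to Day 59 and still gives 59 - 51 + 1 = 9 days. Rescue that begins and ends before Day 51 would show only in the supportive version.

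### Every taper endpoint in SAP 10.1.5 drops diary days after a missed infusion, with no version that keeps them, so one missed infusion can turn a full taper success into a 115-day failure

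*SAP*

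**What the plan says.** SAP 10.1.5 defines one endpoint for ability to taper and seven for maintaining the taper (2a to 2g). They include "Taper OCS dose level down to 5mg/day or less at any time and remained for at least 90 consecutive days", "Taper OCS dose level down to 5mg/day or less at any time and remained for at least 115 consecutive days", and a time to first relapse, "Defined as the duration from the first day of hitting 5mg (plus 5 consecutive days) to when >5mg is needed". The section closes with a rule on missed infusions. Its scope is "In each of the above endpoints, when study drug dosing is missed", and its content is "OCS diary data >30 days after previous study drug infusion will be ignored until dosing restarted". It therefore covers endpoint 1 and all of 2a to 2g.

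OCS burden is handled differently. SAP 10.1.3 calculates the time-adjusted AUC with no missed-dose window. SAP 10.1.4 then says that "analyses will be repeated, but excluding a window around a missed dose of study treatment", so both versions are reported.

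Endpoint 2g looks like an all-data version: "Proportion of days at 5mg or less including all diary days (i.e. even those when OCS dose was increased >5mg for non-sarcoidosis events". Its parenthesis restores only increases made for non-sarcoidosis reasons, and the closing rule still applies to it.

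The protocol's secondary endpoint is the number of patients who reach 5 mg/day and hold it through Week 24. It carries no missed-dose exclusion. SAP 3.3, which summarises changes from the protocol, records the move to the end of the dosing period (30 days after the last dose) but not this exclusion.

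**The concern.** The rule removes recorded outcome data because of something that happens after randomisation, and no taper analysis leaves those data in. The SAP also does not say what ignoring a day means for a count of consecutive days. The gap could end the run, or it could be skipped so that the run continues with fewer counted days. The first can score an unbroken taper as broken. The second can leave a run too short and can hide an increase above 5 mg.

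Missed infusions with a later restart are foreseen. Protocol 6.3.1 makes COVID-19 allowances, 6.4.1 requires discontinuation only after two consecutive missed doses, and 6.5 counts five of six doses as completing the study. The arms are small: 8 planned patients per active dose against 12 pooled placebo patients, compared by Fisher's exact test for 2a to 2d. One reclassified patient moves a responder rate by 1/8 = 12.5 points in an active arm, or 1/12 = 8.3 points in pooled placebo.

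**Working it through.** The plan gives no figure for the effect of this rule, so there is none to reproduce. The check is a count of days on the planned calendar.

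**Inputs**
- Infusions on Days 1, 29, 57, 85, 113 and 141 (Protocol 4.1.2 and Table 1).
- Taper starts on Day 15 and is complete by Day 50 (Protocol 4.1). Day 15 is the earliest day at 5 mg and Day 50 the latest planned.
- Scheduled end of study is Day 169. The SAP 3.3 dosing period ends on Day 141 + 30 = Day 171, used as a check.
- Diary days are kept through 30 days after the last infusion given and resume on the day of the next one (SAP 10.1.4 and 10.1.5).

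**Days dropped.** If the last infusion was on Day p and the next on Day r, Days p + 31 to r − 1 are dropped, which is r − p − 31 days. For one missed mid-study infusion r − p = 56, so 56 − 31 = 25 days. If Week 12 (Day 85) is missed, Days 88 to 112 are dropped.

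**Patient A: 5 mg every day from Day 50 to Day 169**, 169 − 50 + 1 = 120 days.

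| Missed | Days dropped | Runs left if the gap breaks the run | Days left if the gap is bridged |
|---|---|---|---|
| Week 4 | 32–56 (7 fall in the run) | 57–169: 113 | 120 − 7 = 113 |
| Week 8 | 60–84 | 50–59: 10; 85–169: 85 | 120 − 25 = 95 |
| Week 12 | 88–112 | 50–87: 38; 113–169: 57 | 120 − 25 = 95 |
| Week 16 | 116–140 | 50–115: 66; 141–169: 29 | 120 − 25 = 95 |

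- 115-day criterion: failed in all four cases on both readings. With follow-up to Day 171, only the Week 4 result changes (113 + 2 = 115, just met).
- 90-day criterion: failed for Weeks 8, 12 and 16 if the gap breaks the run (85, 57, 66). Met in every case if bridged.

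Week 20 is set aside. If that infusion is missed, the last dose is on Day 113 and the dosing period itself ends on Day 143, so the exclusion changes nothing.

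**Patient B: 5 mg every day from Day 15 to Day 169**, 155 days.
- Gap breaks the run: the longest run is 113, 85, 73 or 101 days for a miss at Week 4, 8, 12 or 16. All are below 115, and Weeks 8 and 12 are also below 90. For Week 12 the two runs are 87 − 15 + 1 = 73 and 169 − 113 + 1 = 57. To Day 171 the Week 4 case again reaches 115.
- Gap bridged: 155 − 25 = 130 days in each case. Both criteria are met.

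**Relapse (2e), Week 12 missed.** An increase above 5 mg that starts and ends within Days 88 to 112 is not counted. One that starts on Day 88 and continues is first counted on Day 113, which is 113 − 88 = 25 days late.

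**With all diary days kept**, Patient A has 120 days and Patient B 155. Both meet the 90- and 115-day criteria after a miss at Week 4, 8, 12 or 16.

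**The case against.** The SAP gives a reason for the window: a missed dose is likely to change OCS use, and excluding the period isolates the treatment effect. That is a legitimate on-treatment question, it fits the half-life argument in SAP 3.3, and the rule is the same in both arms. Choosing between it and an all-data analysis is partly a choice of estimand. This stands as a reason to keep the excluded version. It does not explain why the taper endpoints have only that version when burden has both.

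Three stronger readings are tempting and not supported.
- A reader might infer that one missed infusion puts 115 days, or 90 days, out of reach for everyone. Patient B passes both with 130 days if the gap is bridged, and Patient A then still meets 90 days after one miss. The text does not choose between the readings.
- A reader might infer that all diary data after a miss are lost. Only about 25 days per single miss are dropped. Those days remain in the 10.1.3 AUC, in the 10.1.6 dose-time plots (which state no exclusion) and in the data listings. An increase that persists past restart is still counted, though late.
- A reader might infer that the comparison is biased towards one arm. The documents give no frequency of missed infusions and nothing on how misses divide between arms, so neither direction nor size can be calculated.

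The stakes are also limited. The primary endpoint is safety, SAP 7.4.1 rules out formal hypothesis testing, and SAP 7.5 calls the tests exploratory.

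**Conclusion.** The concern holds in a bounded form. The missed-dose exclusion applies to every taper endpoint with no unexcluded counterpart, and the treatment of ignored days within a consecutive run is undefined. A patient who reaches 5 mg on the latest planned day and stays there to Day 169 is scored a 115-day failure after one miss at Week 4, 8, 12 or 16, whether the gap breaks the run or is skipped. The exception is the Week 4 case followed to Day 171. Failure at 90 days after one miss, and failure at 115 days by a patient at 5 mg from Day 15, require the gap to break the run. Some relapses can be missed, or dated up to 25 days late.

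These results assume infusions on the planned days and a complete diary. A third treatment, in which the gap neither breaks nor shortens the run, would credit Patient A with 120 days. The SAP does not state it, and it would count days that the rule says to ignore. The effect on the trial's results cannot be estimated from the documents. This is a worthwhile, inexpensive correction to exploratory analyses of a protocol secondary endpoint, and does not touch the primary safety analysis.

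**What to change.** - For endpoints 1 and 2a to 2g, add an analysis without the missed-dose exclusion. Use all recorded diary days within the analysis period (to the end of the dosing period), and keep the existing non-sarcoidosis rules in 2e and 2f. Present it beside the excluded version, as 10.1.3 and 10.1.4 do for burden.
- In the excluded version, state whether ignored days break a run and, separately, whether they count towards its length. Ruling out a break is not enough, because Patient A still falls short of 115 days when the gap is bridged.
- List the exclusion in SAP 3.3 as a change from the protocol endpoint.

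The cost is one more run of existing programs, an extra set of tables and a few sentences in the SAP. No new data are needed.

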5. STUDY POPULATION

A total of 36 patients with pulmonary sarcoidosis (24 randomized to ATYR1923 and 12 to placebo) are planned to be randomized in the study.

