5. STUDY METHODS

5.1. General Study Design and Plan

As background for the statistical methods presented below, this section provides an overview of the study design and plan of study execution. The protocol is the definitive reference for all matters discussed in what follows.

This randomized, double-blind, placebo-controlled, study will evaluate the safety, tolerability, immunogenicity, PK, and preliminary efficacy of multiple ascending doses of IV ATYR1923 in patients with pulmonary sarcoidosis undergoing a protocol-guided oral corticosteroid (OCS) tapering regimen.

This study will consist of 3 staggered multiple dose cohorts. Each eligible patient will participate in only one cohort during the study. Within each cohort, 12 patients will be randomized 2:1 (block size of 6) to ATYR1923 (N=8) or placebo (N=4). Study drug will be administered via IV infusion every 4 weeks for a total of 6 doses (20 weeks of treatment). The follow-up study visit is scheduled for 4 weeks after the last infusion. The ATYR1923 doses levels to be evaluated are 1.0 mg/kg, 3.0 mg/kg, and 5.0 mg/kg.

Day 1 is the calendar day of first infusion.

Starting on Day 15, patients will begin a taper (reduction) in OCS (per the ATYR1923-C-002 Oral Corticosteroid Taper Guidelines) from their starting dose of 10-25 mg/day of prednisone (or equivalent) to a target dose of 5 mg/day, to be completed on or before Day 50. The OCS dose will be tapered by 5.0 mg/day every 1 to 2 weeks, depending on the starting dose. Smaller incremental titrations to the target dose of 5 mg/day by Day 50 may be implemented per Investigator judgement. Patients will be maintained at the target dose of 5.0 mg/day (or equivalent) through Week 24/End-of-Study (EOS). Optionally, further titrations in the OCS dose to below 5 mg/day may be attempted after the Week 16 visit, if determined by the Investigator to be feasible.

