8. SUMMARY OF STUDY DATA

Unless otherwise specified, summaries will be presented by treatment arms, presenting all active arms individually, in addition to combined placebo arm and combined active arm.

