10.1.3. Time adjusted OCS Burden

Time adjusted AUC is a measure of steroid burden and approximates the mean steroid usage post-baseline for each patient. For each patient, it is calculated and summarized as follows,

$$Time\ Adjusted\ AUC = \sum_{t=M}^{N-1} \frac{AUC}{N-M} = \sum_{t=M}^{N-1} \frac{(C_t + C_{t'}) (t' - t)}{2(N-M)},$$

where

C_x is the OCS dose in mg on day x ,

t' is the study day of the next known OCS daily dose after day t ,

M and N are start and end study days of the analysis periods of interest. In this study, we are interested in the time periods a) Day 1 through end of dosing period (30 days after last dose) or day of last known OCS dose (if earlier than end of dosing period) and b) Day 51 through end of dosing period (30 days after last dose) or day of last known OCS dose (if earlier than end of dosing period).

Similarly, change from baseline and percent change from baseline at each diary entry will be used as C_x in the formula above, and analyses will be repeated.

aTyr Pharma, Inc.
Study ATYR1923-C-002 Statistical Analysis Plan
IND#: 133692

FINAL Version 1.0
2021-08-02

In addition, active treatment arm for each cohort and combined active arm are compared to combined placebo using the following pseudo code.

```
proc glm data = auc;  
  class treatment(ref=Placebo);  
  model auc = treatment baselineOCS / solution;  
  lsmeans treatment / pdiff=control("Placebo") adjust=T cl;  
run;
```

The difference between LS means, 95% Confidence Intervals and p-values will be presented.

Time adjusted AUC for Day 1/51 through end of treatment periods will be summarized using density and box plots by treatment.

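### The Fisher tests on maintaining the 5 mg/day taper compare only single active arms with placebo, although every other tested steroid endpoint also has a combined-active comparison.

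*SAP*

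**What the plan says.** SAP 10.1.5 lists one endpoint called Ability to Taper and seven called Maintain Taper (2a to 2g). Endpoints 2a to 2d ask whether the patient reached 5 mg/day or less at any time and stayed there for at least 30, 60, 90 or 115 consecutive days. The test is introduced with "For each of the first 4 taper maintenance endpoints above" and is specified as a "2-sided Fisher" test. The comparison is then limited: the "exact test will be performed between each individual active treatment arm and combined placebo". The pseudo code agrees, since it subsets the data to one active arm and placebo.

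The neighbouring analyses are set up differently:

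- Time to first relapse (2e): "A log-rank test will be performed between each individual/combined active treatment arm and placebo to obtain p-values versus placebo".
- Proportion of days at 5 mg or less (2f, 2g): the Wilcoxon test is likewise planned for individual and combined active arms.
- Time-adjusted AUC (SAP 10.1.3): each cohort's active arm and the combined active arm are compared with combined placebo. The study-drug-adjusted version in SAP 10.1.4 follows the same scheme by reference.
- The MMRM and RCRM for lung function (SAP 11.1.1.1 and 11.1.1.2) also include the combined active arm.

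For summaries, SAP 8 sets a default of showing each active arm "in addition to combined placebo arm and combined active arm". SAP 7.4.1 and 7.5 say that there is no formal hypothesis testing, that the tests are exploratory, and that no multiplicity adjustment is made.

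**The concern.** The four responder endpoints are the only tested steroid endpoints without a pooled comparison, and nothing in the SAP explains why. The log-rank and Wilcoxon paragraphs, which do include the combined arm, follow directly after the Fisher paragraph, so this looks like a drafting slip rather than a choice.

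Two things are at stake. First, an exact test of 8 against 12 can reach a small p-value only for very large differences, and for some plausible results it cannot reach one at all. Second, if a pooled p-value is wanted later, SAP 3.2 would class it as a post-hoc analysis, although the same comparison is pre-specified for the sibling endpoints.

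**Working it through.** **Plan's own figure.** There is none to reproduce: SAP 6 and Protocol 10.1.3 state that no power calculation was made.

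**Inputs.**

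- Arm sizes: each cohort has 8 active and 4 placebo patients (SAP 5.1). Over three cohorts, 3 × 8 = 24 and 3 × 4 = 12, which matches Protocol 5: "24 randomized to ATYR1923 and 12 to placebo". A single-arm test is therefore 8 v 12 and a pooled test 24 v 12.
- Level: none is stated for the Fisher tests. Two-sided 0.05 is assumed, in line with SAP 10.1.3, where "95% Confidence Intervals and p-values will be presented".
- Response rates: none are given. A range is assumed.

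**Formula.** With n1 active and n2 placebo patients and true rates p1 and p2, exact power is the sum over all i = 0…n1 and j = 0…n2 of Bin(i; n1, p1) × Bin(j; n2, p2), counted only where the two-sided Fisher p-value for i/n1 v j/n2 is ≤ 0.05.

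**Same rate at every dose.**

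| Active / placebo rate | 8 v 12 | 24 v 12 |
|---|---|---|
| 60% / 20% | 0.318 | 0.578 |
| 60% / 30% | 0.163 | 0.316 |
| 70% / 30% | 0.298 | 0.532 |
| 80% / 30% | 0.492 | 0.769 |
| 80% / 40% | 0.316 | 0.557 |
| 80% / 50% | 0.174 | 0.344 |
| 90% / 50% | 0.341 | 0.696 |

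**What results can reach p ≤ 0.05.**

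- 8/8 active v 6/12 placebo (6 non-responders among 20): the observed table has C(12,6) = 924 of C(20,6) = 38,760 arrangements. The less likely tables in the other tail add 672 + 28. So p = 1,624/38,760 = 0.042.
- 8/8 active v 7/12 placebo (5 non-responders among 20): C(12,5) = 792 of C(20,5) = 15,504, plus 56 from the other tail. So p = 848/15,504 = 0.055. Even a perfect active arm misses 0.05.
- Pooled, 22/24 v 7/12 (7 non-responders among 36): (276 × 792 + 24 × 924 + 792)/8,347,680 = 241,560/8,347,680 = 0.029.

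With 7, 8 or 9 placebo responders the pooled arm can still reach 0.05, needing 22/24, 23/24 and 24/24. With 10 or more, neither test can.

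**Effect at the top dose only.**

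| Rates at 1, 3, 5 mg/kg | Placebo | Pooled 24 v 12 | Top dose 8 v 12 |
|---|---|---|---|
| 20%, 20%, 80% | 20% | 0.145 | 0.686 |
| 30%, 30%, 80% | 30% | 0.109 | 0.492 |

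**Three single-arm tests taken together.** With 70% at every dose v 30% placebo, the chance that at least one of the three reaches 0.05 is 0.552, against 0.532 for the one pooled test. With 30% everywhere (no effect) the corresponding chances are 0.054 and 0.027.

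**The case against.** The case on the other side is substantial, and most of it limits the point without removing it.

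- *The pooled result is not lost.* SAP 10.1.5 summarises counts and percentages, and SAP 8 makes a combined active column the default. This stands: only the test is missing. The SAP 8 rule governs summaries, so the Fisher sentence does not breach it.
- *Power is the wrong yardstick for an exploratory study.* The plan claims no power and states no level. This stands, and it keeps the point minor. It does not explain why one group of endpoints is treated differently.
- *Pooling is not always better.* In an ascending-dose study the effect may sit at the top dose, and then pooling dilutes it. This stands. A reader might infer that 24 v 12 is the most informative comparison, but the documents do not establish that.
- *The three single-arm tests together find something about as often as the pooled test when effects are equal.* True in the case computed, but with about twice the chance of a false signal (0.054 v 0.027), and without answering whether active treatment as a whole differs from placebo.

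Three stronger readings are tempting and go too far. First, that every other steroid endpoint has a pooled comparison: Ability to Taper has no test for any arm, and the dose-time profiles in SAP 10.1.6 are shown by cohort. Second, that Ability to Taper should therefore be tested too: the SAP confines the Fisher test to 2a to 2d, and no inconsistency supports an extension. Third, that 2a to 2d are the protocol's secondary endpoint itself: that endpoint requires maintenance through Week 24 (in the SAP, through the end of the dosing interval), whereas 2a to 2d count runs starting at any time. Only the 115-day run comes close, since Day 50 to Day 169 is 119 days.

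**Conclusion.** The inconsistency is real. Endpoints 2a to 2d are tested arm by arm only, while all other tested steroid endpoints add the combined active arm, and no reason is stated. If the effect is similar at 1, 3 and 5 mg/kg, the omitted comparison would have roughly one and a half to two times the power of any one planned test in the scenarios tabulated, and it would remain capable of a small p-value at 7 to 9 placebo responders, where no single arm is. If the effect is confined to the top dose, the pooled test is much weaker than the top-dose test.

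These sizes rest on assumed response rates, an assumed 0.05 level and the planned 8, 24 and 12 patients. Undosed or replaced patients, and exclusions from the EE Set, would shift them. Neither the primary safety objective nor any formal inference is affected. A reader might infer that power is being given up at no cost. The documents do not support that: the gain is conditional on dose, and the extra p-values are unadjusted.

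**What to change.** In SAP 10.1.5, extend the Fisher sentence for endpoints 2a to 2d to the individual/combined wording that the log-rank sentence already uses, against combined placebo. Add pseudo code in which the three active arms form one group. Keep the single-arm tests. Alternatively, state why the combined arm is left out.

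No data, visits or patients are needed. The cost is one further test for each of four endpoints. SAP 10 runs the steroid analyses in both the mITT and EE Sets, so 4 × 2 = 8 unadjusted p-values are added to the 3 × 4 × 2 = 24 already planned. To count as pre-specified, the change has to be made before unblinding. After that, SAP 3.2 requires it to be identified as post hoc.
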